5.1 Primary Objective

The primary objective of this pilot study is to evaluate the safety, feasibility, and efficacy of the product (3M™ Cavilon™ Advanced Skin Protectant) when used on damaged skin around an ostomy, drain or fistula.

6. Study Design

This is a pilot study evaluating the product, 3M[™] Cavilon[™] Advanced Skin Protectant, for the management of skin around an ostomy, drain and/or fistula. All subjects will receive the product for up to 14 days.

6.1 Randomization

This is a pilot study with no randomization.

6.2 Blinding

Blinding is not needed for a single product study.

6.3 Sample Size

A maximum of 30 subjects (10 subjects each for ostomy, drain and fistula) will be enrolled. A sample size of 30 is usually sufficient to estimate the distribution of a population and provide an estimate of performance for future studies.

Page 15 of 43 Status: Release Version: 1

Issue Date: 10/5/2016 9:39:53 AM

6.4 **Study Duration**

In order to screen, enroll, and complete up to 30 evaluable subjects, an enrollment period of is anticipated. 3M™ Cavilon™ Advanced Skin Protectant is indicated for application every 72 hours. Patient will return or be seen inpatient every 72 hours (±24 hours) for evaluation of product application. Assessment of denuded surface area will be measured at baseline. follow-up visits, and at the end of the study typically at day 14 but may be sooner if wound resolves at an earlier date. As previously noted, each subject may be followed for up to 14 days.

6.5 Primary Efficacy Endpoint

The primary endpoint includes the improvement in skin condition (denuded skin) at the primary site and pain score (using Faces Pain Visual Analog Scale) from baseline to the end of the study.

6.6 **Secondary Efficacy Endpoints**

6.7 Safety Endpoints

Assessment of the safety of the product will be based upon analyses of the number and percent of subjects with an adverse event (AE) and the nature of each AE. The data will be summarized based on the number and percent of subjects reporting AEs. In addition, AEs will be categorized and then summarized by relation to product and severity/intensity. Incidence of discontinuation will be summarized by reason for discontinuation.

7. **Study Population**

Subjects will meet the Inclusion/Exclusion criteria set forth in Section 7.1 and 7.2.A

7.1 Subject Inclusion Criteria

Subjects may be enrolled into this study if the answers to all these questions are **yes**.

- 1. Is the subject 18 years of age or older?
- 2. Does the subject have red skin with **breakdown** (i.e. skin erosion and denudation or denudation of skin alone) at the site of an ostomy, drain site, or fistula?
- 3. Is the subject willing to have photos taken of their skin and permit use of photographs in potential publication?
- 4. Is the subject willing to release rights to 3M for the use of the photos?
- 5. Is there a reasonable expectation that the subject will be in the hospital or available for follow-up visits during the 14 day study period?

Page 16 of 43 Status: Release Version: 1

Issue Date: 10/5/2016 9:39:53 AM

6. Has the subject, signed an Institutional Review Board-approved informed consent/assent document and authorized the use and disclosure of protected health information?

7.2 Subject Exclusion Criteria

Subjects are excluded from participation in this study if **any** of the answers to these following questions is yes.

- 1. If female, is the subject pregnant or breast feeding or has she given birth within the 3 weeks preceding the screening visit?
- 2. Does the subject have a known allergy to acrylates or cyanoacrylates?
- 3. Does the subject have a preexisting skin disease on the areas affected that may make skin assessments for this study difficult?
- 4. Does the skin area affected require treatment with a concomitant medication or product?
- 5. Has the subject received antifungal powders in the area affected within 24 hours prior to enrollment?
- 6. Has the subject received cyanoacrylate based skin protectant (such as Marathon) within 72 hours prior to enrollment?
- 7. Does the subject have any medical condition that in the opinion of the investigator should exclude him/her from participating in the study?
- 8. Has the subject been enrolled in any investigational study where product was applied to proposed study sites within 30 days of the screening visit?

8. Subject Consent

The Investigator must ensure that written informed consent to participate in the study is obtained before including any individual as a subject in the study, and before conducting any study-related assessments. The Investigator must provide the prospective subject, with sufficient opportunity to consider whether or not to participate, and minimize the possibility of coercion or undue influence. The process is designed to 1) give the subject all the information that he/she needs, 2) ensure that the subject understands the information and 3) give the subject a chance to consider study participation. The process should permit the subject to ask questions and exchange information freely.

Specifically, the Investigator is to explain to each subject all elements of informed consent as specified in 21 CFR 50.25. This also includes explaining that photographs will be taken and may be used in publications in ways that do not identify the subject. After the explanation, the subject will voluntarily sign and date the consent/assent form if they wish to participate in the study. A copy of the consent/assent form must be provided to the subject. A signed and dated copy of the consent/assent form must be maintained in the Investigator Site File at all times. A sample consent form is provided in Appendix E. The informed consent process must be followed, and the subject's participation in the study, must be documented in the subject's medical record/chart.

Page 17 of 43 Status: Release Version: 1

Issue Date: 10/5/2016 9:39:53 AM

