8.3 Confidentiality of Data

The Principal Investigator will oversee the conduct of the study and all data will be kept confidential. Confidentiality will be maintained by using patient identification numbers instead of names. Consent forms, data collection sheets and records, linking a subject's name with their ID number will be maintained in a locked cabinet or locked office. Information to be stored on the computer will be identified by subject ID and will be password protected. Data disclosed outside the study team will be de-identified or will only include general group demographic information. Protected Health Information and/or identifiable study data will not be shared with anyone outside the study team or Health System, with the exception of the study sponsor, and federal regulators/ institutional officials for the purposes of auditing.

Page 18 of 43 Status: Release Version: 1

Issue Date: 10/5/2016 9:39:53 AM

Subject medical information obtained by this study is confidential, and disclosure to third parties other than those noted below is prohibited.

Upon the subject's permission, medical information may be given to his or her personal physician or other appropriate medical personnel responsible for his or her welfare.

Data generated by this study must be available for inspection upon request by representatives of the U.S. FDA, national and local health authorities, the device manufacturer, and the IRB.

9. Screening and Enrollment

A representative from the site will complete the following screening and enrollment activities:

- Obtain Informed Consent
 - Explain the study to the subject, answer questions, and obtain written informed consent
- Review the Inclusion/Exclusion Criteria
- Perform assessments required by the Inclusion/Exclusion criteria
 - Collect urine sample and perform urine pregnancy test for female subjects who are of childbearing age. If the subject is post-menopausal, no pregnancy test is required.

If a subject does not meet all the Inclusion/Exclusion criteria, the subject will be excluded from the study.

If a subject meets all the Inclusion/Exclusion criteria, the Investigator, study nurse, or research staff (when appropriate) will complete the following remaining screening activities:

- Record subject demographics.
- Obtain and record history.
- Obtain and record information describing current medications and treatment

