13.1 Study Product

3M will label, package, and ship the investigational product to each research facility participating in the study. Each study product will be labeled with the following minimum information:

Study Number EM-05-013620

- 3M Health Care, St. Paul, MN 55144-1000
- 3M™ Cavilon™ Advanced Skin Protectant
- Lot number
- Package content: single-use applicator with ampoule
- Non-sterile Solution. Applicator is sterile if package is intact
- Use as directed in protocol. See Instructions for Use.
- DANGER! HIGHLY FLAMMABLE!
- Store at room temperature

Page 23 of 43 Status: Release

Version: 1

Issue Date: 10/5/2016 9:39:53 AM

Expiration date
 Instructions for Use (IFU) is provided in Appendix A.

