15.2 Risk Minimization Actions

Additional risks may exist. Measures which have been taken to minimize risks include:

- The selection of Investigators trained in management and prevention of skin related issues around ostomies/drains and fistulas.
- Specific Investigator and study nurse training on the use of the product
- A well-defined clinical protocol, including specific inclusion/exclusion criteria, to enroll
 appropriate subjects in the study

Risks can be minimized at the clinical site through:

- Compliance with this protocol
- Performing assessments in the appropriate hospital environment
- Adherence to subject inclusion/exclusion criteria
- Close monitoring of the subject's status during follow-up

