- Make no changes in or deviate from this protocol, except to protect the life and physical
 well-being of a subject in an emergency; document and explain any deviation from the
 approved protocol that occurred during the course of the clinical study.
- Create and maintain source documents throughout the clinical study and ensure their availability with direct access during monitoring visits or audits; ensure that all clinical study-related records are retained per requirements.
- Ensure the accuracy, completeness, legibility, and timeliness of the data reported to the sponsor in the CRFs and in all required reports.
- Record, report, and assess every adverse event.
- Report to the IRB any SAEs, and supply 3M with any additional information related to the safety reporting of a particular event.
- Maintain the product accountability records and control of the product, ensuring that the study product is used only by authorized/designated users and in accordance with this protocol and Instructions for Use.
- Allow 3M or designee to perform monitoring and auditing activities, and be accessible to the monitor and respond to questions during monitoring visits.
- Allow and support regulatory authorities and the IRB when performing auditing activities.
- Ensure that informed consent is obtained in accordance with this protocol and local IRB requirements.
- Inform the subject of any new significant findings occurring during the clinical study, including the need for additional medical care that may be required.
- Ensure that clinical medical records are clearly marked to indicate that the subject is enrolled in this clinical study.
- Ensure that the center facilities and study team are adequate and are maintained and documented for the duration of the clinical study.

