APPENDIX A- Instructions for Use of 3M™ Cavilon™ Advanced Skin Protectant

3M™ Cavilon™ Advanced Skin Protectant

Product Description:

3M™ Cavilon™ Advanced Skin Protectant is a polymeric-cyanoacrylate solution intended for the protection of intact or damaged skin. Upon application to skin, the liquid dries rapidly to form a primary long-lasting waterproof, highly durable film barrier. It is elastomeric, adhering to the contours of the skin and providing a uniform film. The film is transparent and possesses good oxygen and moisture vapor permeability.

The polymer-cyanoacylate is dispersed in a non-stinging solvent. The film is colorless, non-cytotoxic and has a low dermatitis potential. The film adheres to dry, moist or wet skin surfaces and remains intact during conditions of continuous or repeated exposure to moisture or caustic irritants. It will wear off the skin and does not require removal.

Ingredients: Hexamethyldisiloxane, Acrylic Tetrapolymer, 2-Octyl Cyanoacrylate

Indications for Use

Cavilon™ Advanced Skin Protectant forms a film barrier intended to protect intact or damaged skin. It is effective in conditions where skin is frequently or continuously exposed to moisture and caustic irritants such as feces, digestive fluids, wound drainage and urine. Cavilon™ Advanced Skin Protectant also can be used in areas exposed to friction and shear from bedding, clothing, shoes or any other material that would rub against the skin.

Contraindications

Cavilon Advanced Barrier Film is NOT to be used:

- as a wound dressing for full thickness wounds
- in or around the eyes

Warnings

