1. DANGER! EXTREMELY FLAMMABLE!

2. Cavilon Advanced Skin Protectant is extremely flammable until it has completely dried on the skin.

Page 36 of 43 Status: Release Version: 1

Issue Date: 10/5/2016 9:39:53 AM

- 3. Cavilon Advanced Skin Protectant should only be applied when no ignition sources or heat-producing devices are in use.
- 4. Avoid using Cavilon Advanced Skin Protectant around flames.
- 5. Use Cavilon Advanced Skin Protectant only in well ventilated area.
- 6. Avoid use on individuals who are allergic to any of the ingredients.
- 7. The product is individually packaged for single use only. Reuse could result in increased risk of infection, or inadequate product performance.
- 8. Cavilon Advanced Skin Protectant is not intended for applications requiring sterile product (e.g. infusion catheter site protection and care or surgical site protection).
- 9. Keep out of the reach of children.

Precautions

- Skin absorption and the effectiveness of topical medications (including: antimicrobials, antifungals, and analgesics) may be reduced or prevented by the presence of the Cavilon Advanced Skin Protectant.
- 2. Use of other barrier products, ointments, creams or lotions may significantly reduce the effectiveness of the product.
- 3. The product can increase the adhesion of some adhesive products.

Directions for Use

- Cleanse skin before applying Cavilon Advanced Skin Protectant. Gently dry areas of intact skin. If areas of erosion (denudement) are present, excess serous or serosanguinous drainage may be blotted with a gauze pad if necessary.
- 2) Grasp applicator and place thumb at the end of the lever. Aim the sponge end of the applicator downward and firmly depress the lever to break the internal ampule. (Figure 1) A snapping or popping noise will be noted as the ampule breaks.

Page 37 of 43 Status: Release

[figure not shown]
Version: 1

Issue Date: 10/5/2016 9:39:53 AM

Figure 1

- 3) Keep the applicator pointed in a downward position for approximately 10 seconds. Fluid will flow into the foam sponge; continued pressure on the lever is not required. Fluid will not completely saturate the sponge to the edges.
- 4) Using an even, sweeping motion, gently wipe the foam sponge across the skin (Figure 2); downward pressure on the applicator is not needed and may result in pooling of fluid. Move to adjacent unprotected area and repeat application until the entire area of concern has been covered.

Page 38 of 43 Status: Release

Version: 1

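### Exclusion 2 asks only about acrylate or cyanoacrylate allergy, while the product's Instructions for Use warn against use with allergy to any ingredient, including hexamethyldisiloxane

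*Combined protocol and SAP*

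**What the plan says.** Section 7.2, exclusion 2, asks: "Does the subject have a known allergy to acrylates or cyanoacrylates". The synopsis repeats the question in the same words. No other inclusion or exclusion question mentions allergy.

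Appendix A reproduces the IFU for the product. Its product description gives "Ingredients: Hexamethyldisiloxane, Acrylic Tetrapolymer, 2-Octyl Cyanoacrylate". Item 6 under Warnings says "Avoid use on individuals who are allergic to any of the ingredients".

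Several other provisions bear on the point:

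- Exclusion 7 lets the investigator keep out a subject whose medical condition, in the investigator's judgement, warrants it.
- Section 20 makes the principal investigator responsible for seeing that the product is used "in accordance with this protocol and Instructions for Use".
- The product label in Section 13.1 carries the line "Use as directed in protocol. See Instructions for Use".
- Section 15.2 lists "Specific Investigator and study nurse training on the use of the product" among the measures to reduce risk.

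**The concern.** The eligibility criteria are where a site decides whom to expose to the product, and Section 15.2 counts specific criteria, and adherence to them, among its risk controls. One would expect the allergy criterion to be at least as wide as the product's own allergy warning. Here it is narrower by one ingredient.

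What is at stake is a subject with a known allergy to that ingredient being enrolled because nobody asked. The protocol itself treats reaction to the product as a live possibility: Section 16 names a skin reaction as an anticipated adverse event, and Section 11 plans for a suspected local allergic reaction. Exposure is also repeated and on broken skin. Section 7.1 requires breakdown at the site, and Section 10.1 schedules applications on Days 0, 3, 6, 9 and 12, with unscheduled ones if needed.

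**Working it through.** No statistical formula applies, and the plan gives no figure to reproduce. The check sets the texts side by side.

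**Step 1: ingredients against the two allergy texts.** The ingredients come from the product description in Appendix A.

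| Listed ingredient | Within exclusion 2? | Within Warning 6? |
|---|---|---|
| Hexamethyldisiloxane | No | Yes |
| Acrylic tetrapolymer | Yes (acrylates) | Yes |
| 2-Octyl cyanoacrylate | Yes (cyanoacrylates) | Yes |
| Total | 2 of 3 | 3 of 3 |

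Hexamethyldisiloxane cannot be read into either named class. Appendix A lists it separately from the acrylic and cyanoacrylate components, and both Section 3 and Appendix A describe the polymer and cyanoacrylate as carried in a solvent.

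**Step 2: does another criterion pick it up?** There are 6 inclusion questions (Section 7.1) and 8 exclusion questions (Section 7.2), so 6 + 8 = 14.

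- Questions about allergy: 1 (exclusion 2).
- Questions naming hexamethyldisiloxane, the solvent or any ingredient of the product: 0.
- Questions under which a known allergy could still be acted on: 1 (exclusion 7). It depends on the investigator's opinion and does not prompt anyone to ask.

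These counts describe the gap in the text. They do not measure risk.

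**Step 3: what happens to such a subject.** There are two cases.

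- *The investigator knows of the allergy.* Exclusion 7 is available, and the Section 20 duty to follow the IFU means the product should not be applied.
- *The investigator does not know.* Nothing in the listed criteria brings the allergy to light, because the one allergy question names two other classes. The subject passes all 14 questions, and neither exclusion 7 nor the IFU duty is triggered.

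The gap therefore lies in the second case: the criteria do not elicit the fact that the safeguards need.

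**The case against.** The strongest reply is that the safeguards already do the work. The IFU is an appendix to this same protocol, the label points to it, staff are trained on the product, and Section 20 makes following it an investigator duty. Naming the acrylate components and leaving the rest to the IFU and clinical judgement is a defensible way to draft. Much of this stands: a site that knows of the allergy has clear grounds to withhold the product. What it does not answer is how the site comes to know. None of these provisions puts a question about this ingredient to the subject.

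Three stronger readings are tempting, and the documents do not support them.

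- *A reader might infer that the protocol contradicts itself,* with the subject eligible under Section 7.2 but untreatable under Appendix A. It does not. Section 7.1 says that qualifying subjects may be enrolled and nothing compels treatment, so declining to enrol or treat satisfies both texts.
- *A reader might infer from Section 9 that history plays no part in eligibility.* There, "Obtain and record history" appears under the steps introduced by "If a subject meets all the Inclusion/Exclusion criteria, the Investigator, study nurse, or research staff (when appropriate) will complete the following". But Section 9 places the assessments needed for the criteria before that decision, and several exclusions, including the allergy question itself, cannot be answered without asking about history. The order of the list shows nothing.
- *A reader might infer that safety rests on staff memory of one warning.* The label, the training and the Section 20 duty are standing safeguards, so that goes too far.

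The public copy also omits the CRFs, the consent form and most of the earlier-study summaries in Section 4. A wider allergy question, or a reason for naming only the acrylate components, could be in any of them. The point is therefore confined to the listed criteria.

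**Conclusion.** The point holds as a minor safety alignment. Exclusion 2 is narrower than Warning 6 by one of three ingredients, and no listed question prompts for that ingredient. A subject with a known hexamethyldisiloxane allergy can pass the criteria unless the investigator learns of it and uses exclusion 7 or the IFU duty.

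Confidence is high for the comparison of texts. The practical consequence is likely to be very small. The documents give no frequency for this allergy, and the cap of 30 subjects supplies none, so no expected number of affected subjects is claimed. Endpoints, analysis and sample size are unaffected.

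The conclusion assumes only that the listed criteria are the complete set and that the ingredient list in Appendix A is the one for the product used.

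**What to change.** Reword exclusion 2 in Section 7.2 and in the synopsis to: *Does the subject have a known allergy to any ingredient of the study product (hexamethyldisiloxane, acrylates, cyanoacrylates)?* Keeping the two classes by name means that nobody now excluded becomes eligible.

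The cost is one question changed in two places, and the same edit to the screening form if it repeats the question. The downside is that at most a very few subjects become ineligible, and the IFU already says not to treat them.

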8.1 Subject Authorization for Use & Disclosure of Protected Health Information (PHI)

Subjects will be consented using a current informed consent form that has been approved by the institutional review board (IRB). Subjects will be allowed adequate time to read the informed consent, discuss the consent with study staff and others (i.e. family members, friends, or any of their health care providers), and have their questions answered prior to signing the informed consent.

The subjects will be presented with the consent form in a private room and will be fully informed of the purpose, study related procedures, cost of the study, if they will be paid to be in the study, potential risks, potential benefits, alternative treatments, how long they are expected to participate, contact information and that participation is fully voluntary. Subjects will have the opportunity to have all questions answered to their satisfaction before signing the consent. The patients will be allowed to think about their participation prior to signing the informed consent form for as long as needed.

Signed informed consent for enrollment in this observational study will be obtained from eligible subjects by the PI, a Sub-I, or a member of the research team.

A copy of the signed Informed consent form will be given to the patient and will be scanned into the patient's medical record.

